1.0 Objectives

1.1 Primary Objective

To estimate the complete remission rate (CRR) by the International Myeloma Working Group (IMWG) criteria within 9 months post salvage auto-transplant with subcutaneous daratumumab and hyaluronidase-fihj plus pomalidomide maintenance therapy starting approximately 3 months post salvage auto-transplant in patients with relapsed myeloma.

1.2 Secondary Objective

To evaluate progression-free survival (PFS).

1.3 Exploratory Objective

To discover the impact of daratumumab and hyaluronidase-fihj plus pomalidomide on graft function and immune reconstitution.

2.0 Background

2.1 Overview of Disease/Maintenance Therapy post salvage ASCT

Treatment for multiple myeloma has changed significantly over the past decade. Induction therapy followed by upfront autologous stem cell transplant (ASCT) with melphalan 200 mg/m² has shown significantly improved progression free survival and quality of life for patients with newly diagnosed multiple myeloma (MM).

Maintenance Therapy:

Furthermore, multiple randomized phase III trials have demonstrated significantly improved PFS and OS with the use of continued lenalidomide maintenance therapy post initial ASCT. However, despite these substantial improvements in therapy, the majority of patients will relapse 3-4 years later (1-7).

Salvage ASCT:

Due to earlier diagnoses and improved therapies, MM patients are living significantly longer and many are eligible for second ASCT that can yield a meaningful duration of remission. On the other hand, other patients may not

undergo ASCT in first remission, either due to aggressive disease which may relapse during 1st line induction therapy (including an IMID) or due to preference. Multiple studies have been conducted evaluating salvage ASCT and all demonstrated chemosensitivity and duration of remission after first ASCT were the most important prognostic factors for subsequent long-term disease control (8-17). For patients undergoing salvage ASCT, either as a second transplant or as a first transplant with previous relapse to induction therapy, no standard maintenance therapy has been established post transplant. In a recent study evaluating the addition of lenalidomide to melphalan conditioning for salvage transplant, complete remission rates in both groups (first ASCT after relapsed disease or second ASCT) is similar at 28%, with time for best response of 16-732 days (18).

Maintenance with Daratumumab and Pomalidomide post salvage ASCT:

IMIDs and proteasome inhibitors have been used post salvage ASCT as maintenance treatment, however cytopenias, toxicities, and resistance due to previous exposure to these drugs, decrease their applicability. The newly FDA approved monoclonal antibody daratumumab has established efficacy as a single agent in relapsed and refractory disease, however is not FDA approved as a maintenance option post autologous stem cell transplant. It is an IgG1 kappa human monoclonal antibody directed against CD38. It induces apoptosis directly through Fc mediated cross linking and immune mediated tumor lysis through complement dependent cytotoxicity, antibody dependent cell mediated cytotoxicity and antibody dependent cellular phagocytosis. Thus its potential role as maintenance therapy post salvage transplant is promising and worthy of investigation.

Daratumumab was approved by the FDA in November 2015 for IV infusion. More recently, in May 2020, FDA approved its subcutaneous formulation, daratumumab/hyaluronidase-fihj. Its advantages include a fixed-dose formulation, short administration time of 3-5 minutes, which is significantly shorter than the currently used IV formulation that is given over hours, and a significant reduction in infusion-related reactions. In the Phase 3 COLUMBA study (19) supporting the approval, daratumumab and hyaluronidase-fihj demonstrated a consistent overall response rate (ORR) and pharmacokinetics and a similar safety profile compared with intravenous daratumumab in patients with relapsed or refractory multiple myeloma. In addition, there was a nearly two-thirds reduction in systemic infusion-related reactions with daratumumab and hyaluronidase-fihj compared to intravenous daratumumab (13 percent vs. 34 percent, respectively).

Pomalidomide is the third-generation immunomodulatory drug (IMiD) that has been approved by the FDA in June 2017 for use in relapsed/refractory multiple myeloma in combination with daratumumab IV based on the results of

EQUULUS trial (20). As most of the myeloma patients eligible for salvage ASCT have been exposed to daratumumab, and are refractory to the 2nd generation IMiD, lenalidomide, we hypothesize that a combination of daratumumab and hyaluronidase-fihj plus pomalidomide will improve the patient accrual, and the disease control.

2.2 Daratumumab

Summary of Relevant Clinical Experience

Several phase I /II and II studies (19-21) in relapsed MM patients (4-5 median prior lines of therapy) with daratumumab as monotherapy have been completed. The phase 1 part of the GEN501 trial demonstrated the 16 mg/kg dose as most efficacious and no dose limiting toxicity was observed at any dose level; part 2 revealed an overall response rate of 36% (at least a partial response) and PFS of 5.6 months with the dose of 16 mg/kg. The SIRIUS phase II study similarly demonstrated ORR of 29% and PFS of 3.7 months. Combination therapy with daratumumab, lenalidomide and dexamethasone in a phase I/II trial (GEN503) in relapsed refractory patients with a prior median of 2 lines of therapy, demonstrated an ORR of 100%, and 18 month PFS of 72% (22).

3.0 Background Drug Information

3.1 Daratumumab Preparation – Subcutaneous

Daratumumab and hyaluronidase-fihj will be provided as a fixed-dose (1800 mg), combination drug product containing rHuPH20 drug substance (2000 U/mL) and daratumumab drug substance (120 mg/mL) in a single vial.

If an IRR develops, then the injection should be temporarily interrupted or slowed downIn the event of a life-threatening injection related reaction (which may include pulmonary or cardiac events) or anaphylactic reaction, daratumumab and hyaluronidase-fihj should be discontinued and no additional daratumumab and hyaluronidase-fihj should be administered to the participant. See [Section 3.1.5](#) for instructions on the management of injection related reactions and local ISRs.

3.1.3 Guidelines for Prevention and Management of Injection Reactions:

All participants will receive the following medications 1 to 3 hours prior to each study drug administration:

- An antipyretic: paracetamol (acetaminophen) 650-1000 mg IV or PO
- An antihistamine: diphenhydramine 25-50 mg IV or PO or equivalent. Avoid IV use of promethazine.
 - After Cycle 6, if a participant has not developed an injection-related reaction and is intolerant to antihistamines, modifications are acceptable as per investigator discretion.

- Administer 20 mg dexamethasone (or equivalent) prior to every daratumumab injection. When dexamethasone is the background regimen specific corticosteroid, the dexamethasone treatment dose will instead serve as pre-medication on daratumumab injection days.
- Dexamethasone is given orally or intravenously prior to the first daratumumab injection and oral administration may be considered prior to subsequent injection.
- If the subject does not experience a major systemic administration-related reaction after the first 3 doses, consider discontinuing the administration of corticosteroids (excluding any background regimen-specific corticosteroid).

Pre-dose administration of a leukotriene inhibitor (montelukast 10 mg PO or equivalent) is optional in Cycle 1 Day 1 and can be administered up to 24 hours before injection as per investigator discretion.

If necessary, all PO pre-infusion medications may be administered out of the clinic on the day of the injection, provided they are taken within 3 hours before the infusion.

3.1.4 Post-dose Medication:

Administer post-injection medication to reduce the risk of delayed injection related reactions as follows:

- Consider administering low-dose methylprednisolone (≤ 20 mg) or equivalent, the day after the injection. However, if a background regimen-specific corticosteroid (e.g. dexamethasone) is administered the day after the injection, additional post-injection steroids are not required, but may be considered by the investigator.
- For participants with a higher risk of respiratory complications (e.g. participants with mild asthma or participants with COPD who have an FEV1 $< 80\%$ at screening or developed FEV1 $< 80\%$ during the study without any medical history) the following post-injection medication should be considered:
 - Antihistamine (diphenhydramine or equivalent)
 - Leukotriene inhibitor (montelukast or equivalent)
 - Short-acting $\beta 2$ adrenergic receptor agonist such as salbutamol aerosol
 - Control medications for lung disease (e.g. inhaled corticosteroids \pm long-acting $\beta 2$ adrenergic receptor agonists with asthma; long-acting bronchodilators such as tiotropium or salmeterol \pm inhaled corticosteroids for participants with COPD)
- In addition, these at-risk participants may be hospitalized for monitoring for up to 2 nights after daratumumab administration. If participants are hospitalized, then an improvement in FEV1 should be performed and documented prior to discharge. If these participants are not hospitalized, then a follow-up telephone call should be made to monitor their condition within 48 hours after all injection. If the participant has not experienced a significant

medical event but is hospitalized overnight only for observation, then the hospitalization should not be reported as a serious adverse event. Investigators may prescribe bronchodilators, H1-antihistamines, and corticosteroids that are deemed necessary to provide adequate supportive care in the event a bronchospasm occurs after participants are released from the hospital/clinic. If an at-risk participant experiences no major injection-related reactions, then these post-injection medications may be waived after 4 doses at the investigator's discretion.

- Any post-injection medication will be administered after the injection has completed.

3.1.5 Management of injection-related Reactions and Local Injection- site Reactions of Daratumumab-SC injection-related reactions :

Injection-related reactions are systemic reactions related to daratumumab administration. Participants should be observed carefully during daratumumab administrations. Trained study staff at the clinic should be prepared to intervene in case of any injection related reactions, and resources necessary for resuscitation (e.g., agents such as epinephrine and aerosolized bronchodilator, medical equipment such as oxygen tanks, tracheostomy equipment, and a defibrillator) must be available at the bedside. Attention to staffing should be considered when multiple participants will be dosed at the same time. If an injection related reaction develops during daratumumab and hyaluronidase-fihj administration, then the administration should be temporarily interrupted. Participants who experience AEs during daratumumab and hyaluronidase-fihj administration must be treated for their symptoms. Participants should be treated with paracetamol (acetaminophen), antihistamine, or corticosteroids, as needed. Intravenous saline may be indicated. For bronchospasm, urticaria, or dyspnea, participants may require antihistamines, oxygen, corticosteroids, or bronchodilators. For hypotension, participants may require vasopressors. In the event of a life-threatening injection related reaction (which may include pulmonary or cardiac events) or an anaphylactic reaction, daratumumab and hyaluronidase-fihj should be discontinued.

Injection-related Reactions Grade 1 or Grade 2:

If the investigator assesses a Grade 1-2 injection related reaction to be related to administration of study intervention, then the daratumumab and hyaluronidase-fihj administration should be interrupted. When the participant's condition is stable, daratumumab and hyaluronidase-fihj administration may be restarted at the investigator's discretion. Refer to the USPI for further details regarding continuation of daratumumab and hyaluronidase-fihj administration.

If the participant experiences a Grade 2 or higher event of laryngeal edema, or a Grade 2 or higher event of bronchospasm that does not respond to systemic

therapy and does not resolve within 6 hours from onset, then the participant must be permanently discontinued from daratumumab and hyaluronidase-fihj treatment.

Injection-related Reactions Grade 3 or Higher:

For injection related reaction AEs (other than laryngeal edema or bronchospasm) that are Grade 3, the daratumumab and hyaluronidase-fihj administration must be stopped, and the participant must be observed carefully until resolution of the AE or until the intensity of the event decreases to Grade 1, at which point the daratumumab and hyaluronidase-fihj administration may be restarted at the investigator's discretion. Refer to the SIPPm for further details regarding continuation of daratumumab and hyaluronidase-fihj administration.

If the intensity of the AE returns to Grade 3 after restart of the daratumumab and hyaluronidase-fihj administration, then the participant must be permanently discontinued from daratumumab and hyaluronidase-fihj treatment.

For injection related reaction AEs that are Grade 4, the daratumumab and hyaluronidase-fihj administration must be stopped, and the participant permanently discontinued from daratumumab and hyaluronidase-fihj treatment.

Recurrent Injection-related Reactions:

If a Grade 3 injection related reaction (or Grade 2 or higher event of laryngeal edema, or a Grade 2 or higher event of bronchospasm) recurs during or within 24 hours after a subsequent daratumumab and hyaluronidase-fihj administration, the participant must be permanently discontinued from daratumumab and hyaluronidase-fihj treatment.

Injection Site Reactions (ISR):

In clinical studies, SC administration of daratumumab was associated with local injection site reactions, such as induration and erythema, in some subjects. The reactions usually resolved within 60 minutes. Local injection-site reactions should be managed per institutional standards.

3.1.6 Blood Typing and Cross-matching Interference

Red cell and platelet transfusions will be required for some patients undergoing maintenance therapy post autologous stem cell transplantation. It has previously been reported that daratumumab binds to CD38 expressed on the surface of red blood cells. Although this additional activity may interfere with blood typing and cross-matching, no AEs related to hemolysis have been reported. In previous trials, patients had their blood types assessed before their first daratumumab infusion. They were also encouraged to carry a card indicating their blood type for the duration of the study. In the event of a positive Coombs

test, individual blood banks used a variety of mitigation methods to safely provide blood products. Blood banks were also made aware that this effect could persist for up to 6 months after cessation of daratumumab treatment.

3.1.7 Injection Reactions

Most biologics carry a risk of injection reactions that typically develop during or shortly after the injection. They vary from mild to potentially life threatening and are commonly associated with various signs and symptoms. The mechanisms by which monoclonal antibodies elicit injection reactions remain unclear.

- Monoclonal antibodies may interact with their molecular targets on circulating blood cells, tumor cells, or effector cells recruited to the tumor site (e.g., rituximab with CD20), thereby promoting the release of inflammatory cytokines.
- Injection reactions may have a hypersensitivity component in which the molecular structure of the drug or a component of the drug formulation is recognized as an antigen by the immune system. IgE mediated events are rare but possible.
- Non-immune mediated hypersensitivities are frequent following monoclonal or polyclonal antibody administration. These reactions resemble immune mediated reactions, but an immune mechanism is not detectable. The majority of these reactions imitate the clinical features of milder immune reactions (erythema, urticaria), but greater severity, even a lethal outcome are possible.

There is no difference between the clinical manifestations of the immune-mediated and non-immune mediated reactions. They both may involve the cutaneous, respiratory, gastrointestinal, or cardiovascular systems. The management of both types of reactions is the same.

In both monotherapy and combination clinical trials, the incidence of any grade infusion reactions was 46% with the first infusion, 2% with the second infusion and 4% with subsequent infusions. The incidence of infusion modification due to reactions was 41%. Severe grade 3 infusion reactions included bronchospasm, dyspnea, laryngeal and or pulmonary edema, hypoxia and hypertension. Less serious infusion reactions that occurred in greater than 5% patients were nasal congestion, cough, chills, throat irritation and vomiting.

When used as monotherapy in clinical trials with 156 patients with relapsed and refractory myeloma, the most frequent serious adverse reactions were pneumonia (6%), general physical health deterioration (3%), and pyrexia (3%). These resulted in delay of treatment for 15% of patients. The below tables are from the United States Product Insert and

describe adverse reactions in >10% of patients who (1) received with SC Daratumumab, and (2) IV Daratumumab.

Adverse Reactions (≥10%) in Patients Who Received DARZALEX FASPRO with Bortezomib, Melphalan and Prednisone (D-VMP) in PLEIADES (package insert, Rev. 5/2020)

Adverse Reaction	DARZALEX FASPRO with Bortezomib, Melphalan and Prednisone (N=67)	
	All Grades (%)	Grades ≥3 (%)
Infections		
Upper respiratory tract infection ^a	39	0
Bronchitis	16	0
Pneumonia ^b	15	7 [#]
Gastrointestinal disorders		
Constipation	37	0
Nausea	36	0
Diarrhea	33	3 [#]
Vomiting	21	0
Abdominal pain ^c	13	0
General disorders and administration site conditions		
Fatigue ^d	36	3
Pyrexia	34	0
Edema peripheral ^e	13	1 [#]
Nervous system disorders		
Peripheral sensory neuropathy	34	1 [#]
Dizziness	10	0
Respiratory, thoracic and mediastinal disorders		
Cough ^f	24	0
Psychiatric disorders		
Insomnia	22	3 [#]
Musculoskeletal and connective tissue disorders		
Back pain	21	3 [#]
Musculoskeletal chest pain	12	0
Metabolism and nutrition disorders		
Decreased appetite	15	1 [#]
Skin and subcutaneous tissue disorders		
Rash	13	0
Pruritus	12	0
Vascular disorders		
Hypertension	13	6 [#]
Hypotension	10	3 [#]

^a Upper respiratory tract infection includes nasopharyngitis, respiratory syncytial virus infection, respiratory tract infection, rhinitis, tonsillitis, upper respiratory tract infection, and viral pharyngitis.

^b Pneumonia includes lower respiratory tract infection, lung infection, pneumocystis jirovecii pneumonia, pneumonia, and pneumonia bacterial.

^c Abdominal pain includes abdominal pain, and abdominal pain upper.

^d Fatigue includes asthenia, and fatigue.

^e Edema peripheral includes edema, edema peripheral, and peripheral swelling.

^f Cough includes cough, and productive cough.

[#] Only grade 3 adverse reactions occurred.

Select Hematology Laboratory Abnormalities Worsening from Baseline in Patients Who Received DARZALEX FASPRO with Bortezomib, Melphalan and Prednisone (D-VMP) in PLEIADES

Laboratory Abnormality	DARZALEX FASPRO with Bortezomib, Melphalan and Prednisone ^a	
	All Grades (%)	Grades 3-4 (%)
Decreased leukocytes	96	52
Decreased lymphocytes	93	84
Decreased platelets	93	42
Decreased neutrophils	88	49
Decreased hemoglobin	48	19

^a Denominator is based on the safety population treated with D-VMP (N=67).

3.1.8 Drug Accountability

Accountability for the drug at all study sites is the responsibility of the sponsor-investigator. The sponsor-investigator will ensure that the drug is used only in accordance with this protocol. Drug accountability records indicating the drug's delivery date to the site (if applicable), inventory at the site (if applicable), use by each patient, and disposal of the drug will be maintained by the site.

Accountability records will include drug receipt/destruction dates, quantities, lot numbers, expiration dates (if applicable), and corresponding registered patient numbers.

All material containing daratumumab will be treated and disposed of as hazardous waste in accordance with governing regulations.

3.1.9 Daratumumab Destruction

Study drug should be destroyed on site according to the institution's standard operating procedure. Be sure to document removal and destruction on drug accountability logs.

3.2 Pomalidomide

Pomalidomide is a thalidomide analogue, which exerts an immunomodulatory, antiangiogenic, and antineoplastic effect by the inhibition of the proliferation and induction of apoptosis of hematopoietic tumor cells, and enhancement of T cell- and natural killer cell-mediated immunity and inhibition of pro-inflammatory cytokine production (e.g., TNF-alpha and IL-6) by monocytes. The cytotoxic and immunomodulatory effects of pomalidomide are mediated by targeting substrate proteins (including Aiolos and Ikaros) for ubiquitination and subsequent degradation. Pomalidomide is available as oral capsules in 1, 2, 3 and 4 mg doses.

Pomalidomide will be administered at 2 mg/day PO once daily on Days 1 to 21 during the 28-day cycle. Pomalidomide dose may be reduced, or the treatment schedule may be modified for the management of the study drug-related toxicities. Pomalidomide may be taken with water. Subjects should not break, chew, or open the capsules. Pomalidomide should be taken without food (at least 2 hours before or 2 hours after a meal).

Dose Modification Instructions for Pomalidomide for Hematologic Toxicities Toxicity	Dose Modification
Neutropenia 
 ANC <500 per mm³ or Febrile neutropenia (fever more than or equal to 38.5°C and ANC <1,000 per mm³) ANC return to more than or equal to 500 per mm³ 	
 Interrupt pomalidomide treatment, follow CBC weekly. Resume pomalidomide at 2 mg daily.

 For each subsequent drop <500 per mm³ Return to more than or equal to 500 per mm³ 	
 Interrupt pomalidomide treatment. Resume pomalidomide at 1 mg less than the previous dose
Thrombocytopenia 
 Platelets <25,000 per mm³ Platelets return to >50,000 per mm³ 	
 Interrupt pomalidomide treatment, follow CBC weekly Resume pomalidomide treatment at 2 mg daily

 For each subsequent drop <25,000 per mm³ Return to more than or equal to 50,000 per mm³ 	
 Interrupt pomalidomide treatment Resume pomalidomide at 1 mg less than previous dose.

Pomalidomide Side Effects

Common (occurring in more than 20% of patients)


● swelling (arm/leg)● fatigue● nerve damage (possible numbness, pain, and/or loss of motor function)● dizziness● fever● skin rash	
● abnormal salts, minerals, and/or acids in the blood (possible weakness, swelling, fatigue, low blood pressure, organ failure, heart problems, changes in mental status, and/or seizure)● constipation	
● nausea● diarrhea● loss of appetite● low blood cell counts (red, white, platelet)● weakness● pain● muscle spasms● difficulty breathing
--	--	--

Pomalidomide may cause low blood cell counts (white blood cells, red blood cells, platelets).

- A low white blood cell count increases your risk of infection (such as viral or fungal pneumonia and/or severe blood infection). Infections may occur anywhere and become life-threatening. Symptoms of infection may include fever, pain, redness, and difficulty breathing.
- A low red blood cell count (anemia) may cause difficulty breathing and/or fatigue. You may need a blood transfusion.
- A low platelet count increases your risk of bleeding (such as nosebleeds, bruising, stroke, and/or digestive system bleeding). You may need a platelet transfusion.

Occasional (occurring in 3-20% of patients)

● headache● anxiety● confusion● chills● difficulty sleeping● itching/dry skin● increased sweating	
● high blood sugar (possible diabetes)● dehydration● weight loss/gain● vomiting● tremors	
● kidney failure● nosebleed● cough● severe life-threatening infection (possible low blood pressure, kidney failure, and/or heart failure)
---	--	--

Frequency Unknown, but between 1-10%

● heart attack/failure● low blood pressure (possible dizziness/fainting)● mental status change● depression	
● walking/balance problems (possible falling)● inflammation of the intestines● mouth blisters/sores (possible difficulty swallowing)● blood in the urine● abnormal liver tests (possible liver damage, yellowing of the skin and/or eyes)	
● broken bone(s)● collapse of bones in the spine● bacteria in the blood● multiorgan failure
---	---	--

Rare but serious (occurring in fewer than 3% of patients)


● inability to urinate● liver failure	
● breakdown products of the cancer cells entering the blood stream (possible weakness, low blood pressure, muscle cramps, kidney damage, and/or other organ damage)	
● allergic reaction
--	---	---

Pomalidomide may cause you to develop another type of cancer (such as acute myeloid leukemia, a type of blood cancer).

Pomalidomide may also cause blood-clotting events (such as deep vein thrombosis, blood clots in the lungs, heart attack, and stroke).

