Subjects will receive pre-injection medications and post-injection medication as outlined in [Sections 3.1.3](#) and [3.1.4](#) respectively. See [Section 3.1.5](#) for instructions on the management of IRR and local ISRs.

5.3 Pomalidomide will be given at 2 mg PO daily from day 1-21 in the 28-day cycle. On day 1 of each cycle, doses may be held if clinically indicated (i.e., active infections) for up to 4 weeks. If longer than 4 weeks, the PI will evaluate and determine if the patient can continue on trial or must be taken off study. After day 1 of each cycle, subsequent doses may be held/skipped if clinically indicated (i.e., active infections) per PI or treating physician's discretion.

Pomalidomide not administered between days 1-21 in the 28 days cycle will be considered a missed dose. Administration may resume after active infection is resolved per PI or treating physician discretion. See section 3.2 for further instructions on toxicity management.

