5.5 Dose Delay

Before each cycle, the patient will be evaluated for possible toxicities that may have occurred after the previous dose(s). Toxicities are to be assessed according to the NCI Common Toxicity Criteria for Adverse Events (CTCAE), version 4.0 (<http://ctep.cancer.gov/reporting/ctc.html>). Each AE should be attributed to a specific drug, if possible, so that the dose modifications can be made accordingly. If multiple toxicities are noted, the dose delays are per PI discretion; refer to guidelines that address the most severe toxicity.

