5.6 Criteria for beginning a subsequent treatment cycle

Treatment with daratumumab will use a cycle length of 28 days. For a new cycle of treatment to begin, the patient must meet the following criteria:

- ANC must be $\geq 1,000/\text{mm}^3$
- Platelet count must be $\geq 50,000/\text{mm}^3$

In addition, all other toxicity considered to be related to treatment must have resolved to \leq grade 1, to the patient's baseline values, or to a level considered acceptable by the physician (e.g., hypokalemia that can be managed by replacements) before a new cycle of treatment may begin.

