5.7 Criteria for delaying a subsequent treatment cycle

If the patient fails to meet the above-cited criteria for initiation of the next cycle of treatment or has any of the below toxicities, dosing should be delayed until recovery.

- Grade 4 hematologic toxicities
- Grade 3 thrombocytopenia with bleeding
- Febrile neutropenia of any grade
- Neutropenia with infection, of any grade
- Grade 3 or higher nonhematologic toxicities with the following exceptions:
 - Grade 3 nausea that responds to antiemetic treatment within 7 days
 - Grade 3 vomiting that responds to antiemetic treatment within 7 days
 - Grade 3 diarrhea that responds to antidiarrheal treatment within 7 days
 - Grade 3 fatigue that was present at baseline or that lasts for <7 days after the last administration of daratumumab
 - Grade 3 asthenia that was present at baseline or that lasts for <7 days after the last administration of daratumumab

The maximum delay before treatment should be discontinued is 6 weeks or at the discretion of the Principal Investigator.

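### The pomalidomide table resumes at a fixed 2 mg after a first neutropenia or thrombocytopenia event, which sends a patient already reduced to 1 mg back up to 2 mg

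*Combined protocol and SAP*

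**What the plan says.** Section 3.2 starts pomalidomide at 2 mg daily on days 1 to 21 of each 28-day cycle. It also allows later reductions for any drug-related toxicity: "Pomalidomide dose may be reduced, or the treatment schedule may be modified for the management of the study drug-related toxicities". The table that follows has one block for each lineage.

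- **Neutropenia, first event** (ANC below 500, or febrile neutropenia with ANC below 1,000): interrupt, then "Resume pomalidomide at 2 mg daily".
- **Neutropenia, each later ANC drop below 500:** "Resume pomalidomide at 1 mg less than the previous dose".
- **Thrombocytopenia, first event** (platelets below 25,000): interrupt, then "Resume pomalidomide treatment at 2 mg daily".
- **Thrombocytopenia, each later drop below 25,000:** resume 1 mg below the previous dose.

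The treatment plan in Section 5 adds no rule on the resume dose. Section 5.3 refers the reader back: "See section 3.2 for further instructions on toxicity management".

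**The concern.** The two first-event rows assume that the patient is still on the 2 mg starting dose. That need not be so. The patient may have been stepped down for drops in the other lineage, or reduced for another toxicity under the general permission in Section 3.2. For such a patient, a fixed 2 mg is a dose increase, prescribed on recovery from a new severe cytopenia.

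What is at stake is patient safety. A reduction made because 2 mg was not tolerated is undone by the very table meant to manage toxicity.

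**Working it through.** **Inputs (Section 3.2).** Starting dose 2 mg. First event in a lineage: resume at 2 mg. Later drop in the same lineage: resume at the previous dose minus 1 mg. Write N for ANC below 500 and P for platelets below 25,000. A result of 0 mg is read as stopping pomalidomide; that is the natural reading, although the table does not state it.

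**Rule as written.** Dose after = 2 if the event is the first in its lineage; otherwise dose before − 1.

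**Rule with the fix.** Dose after = the smaller of dose before and 2 if the event is the first in its lineage; otherwise dose before − 1.

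**Two events from 2 mg.** NN and PP give 2, 1. NP and PN give 2, 2. The dose rises in 0 of 4 orders.

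**Three events from 2 mg (resume doses in mg after each event).**

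| Order | As written | With the fix |
|---|---|---|
| NNP, PPN | 2, 1, **2** | 2, 1, 1 |
| NPN, NPP, PNN, PNP | 2, 2, 1 | 2, 2, 1 |
| NNN, PPP | 2, 1, stop | 2, 1, stop |

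The dose rises in 2 of 8 orders as written and in none with the fix. The rise is (2 − 1)/1 = 100%.

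**Four events from 2 mg.** NNPN, NNPP, PPNN and PPNP give 2, 1, 2, 1 as written and 2, 1, 1, stop with the fix. That is 4 of 16 orders. However, NNNN, NNNP, PPPN and PPPP have already stopped at the third event, so only 16 − 4 = 12 orders reach a fourth dosing decision, and the reachable share is 4 of 12. These four are the two three-event orders above with one more event added, not a new mechanism.

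**Already at 1 mg for another toxicity.** The first N or the first P gives 2 mg as written and 1 mg with the fix.

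**Febrile neutropenia.** The first neutropenia row also covers febrile neutropenia with ANC below 1,000, but the repeat-drop row is triggered only by ANC below 500. A patient at 1 mg after two ANC drops who then has febrile neutropenia with ANC 500–999 therefore matches only the first row and is sent to 2 mg. This path lies outside the counts above. The fix gives 1 mg.

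**Search for a rule that overrides the table.**

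- Section 5.3 lets doses be held or skipped and then points back to Section 3.2.
- Section 5.5 says "Each AE should be attributed to a specific drug, if possible, so that the dose modifications can be made accordingly". For multiple toxicities it gives the PI discretion over delays and refers to the guidance for the most severe toxicity. For a severe cytopenia attributed to pomalidomide, that guidance is this table.
- Section 5.6 sets count thresholds: "For a new cycle of treatment to begin, the patient must meet the following criteria", namely ANC at least 1,000 and platelets at least 50,000.
- Section 5.7 says "dosing should be delayed until recovery".

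Sections 5.6 and 5.7 decide when treatment restarts. None of these sections says at what dose, and none bars re-escalation.

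**The case against.** The best defence is that 2 mg is the only assigned dose, so each first-event row simply means resume unchanged. On this view the table is silent about patients already reduced and does not plan to escalate them. The sentence before the table lets the investigator reduce for drug-related toxicity, so staying at 1 mg complies with the protocol. Pomalidomide is interrupted first, and restart waits for ANC of at least 500 or platelets above 50,000, with the stricter Section 5.6 thresholds before a new cycle. The dose never exceeds the starting dose. The cross-lineage path needs three severe events in one patient, and no rate is given for any path.

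Much of this stands. The intent was probably to resume unchanged, the safe choice is permitted, re-dosing into an unresolved cytopenia is prevented, and the situation is probably uncommon. The order counts say nothing about how often it will arise.

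None of it changes what the rows instruct. The permission to reduce is optional, whereas the table row is specific and names 2 mg. The recovery thresholds govern timing, not dose. Reading the repeat-drop rows as covering either lineage does not work either, because each sits under its own heading with its own ANC or platelet threshold.

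**Conclusion.** The concern holds. Both first-event rows give the wrong dose when applied to a patient already at 1 mg: 2 mg daily, a 100% increase, on recovery from a new severe cytopenia. From a 2 mg start this occurs in 0 of 4 two-event orders, 2 of 8 three-event orders and 4 of 12 reachable four-event orders. It also occurs at the first cytopenia of either type in a patient already at 1 mg for another toxicity, and in the febrile neutropenia case described above.

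The conclusion assumes that the table is followed literally and that each block applies to its own lineage. Frequency cannot be estimated from the documents. This is a dosing-safety correction that should be made. It has no bearing on the sample size, the power, or the definitions of CRR and PFS.

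**What to change.** In both first-event rows, replace the fixed 2 mg with an instruction to resume at the dose the patient was taking just before the interruption, and no higher than 2 mg. Keep the 1 mg step-down for each later drop in the same lineage. Add one sentence stating that a patient who would need less than 1 mg stops pomalidomide. Events need not be counted across lineages.

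The cost is two reworded rows and one sentence in an amendment, with no added patients, visits or tests. Every path without a re-escalation keeps its current doses. The downside is lower pomalidomide exposure in the few patients who would have been re-escalated. They stay at 1 mg, and a further drop in a lineage that has already had an event stops the drug, where the current text would step them from 2 mg to 1 mg.
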